Official Title: The effect of an adductor longus tenotomy on the bent knee fall out test

Document Date: February 11th, 2020.

INTRODUCTION

Adductor-related groin pain is the most common type of groin pain in athletes,[1,2] and pain at the proximal adductor longus insertion is a key finding in the diagnosis of longstanding groin pain.[3] “Tightness” or “shortening” of the adductor longus is considered both a cause and effect of pain,(ref) that can lead to increased tension at the proximal insertion, thus playing a role in the persistency of longstanding adductor-related pain. For patients who do not respond sufficiently to non-surgical procedures, an adductor longus tenotomy is a surgical option that is considered to reduce tension at the proximal adductor longus insertion assisting in reduction of pain and return to sport.

The bent knee fall out test (BKFO) is one of the most commonly used tests to test adductor flexibility.[4–6] This test involves a combined hip movement with hip flexion, abduction, and external rotation, and a high result is generally considered to be related to adductor muscle “tightness”, specifically that of the adductor longus.(refs) It is uncertain whether the BKFO test is actually measuring adductor muscle flexibility or hip joint range of motion, as the test results may also be affected by a femoral head cam morphology.[7] A slightly different test, called the Patrick FABER’s test, involves a similar movement and is mainly used as a hip joint pain provocation test.

By cutting the adductor longus tendon thereby removing the effect of potential adductor longus “tightness”, we will be able to show if and how much the flexibility of this muscle effects the test results, to assist in future considerations of what this test is actually testing.

Our aim was to investigate the immediate effect of an adductor longus tenotomy on the results of the bent knee fall out test.

METHODS

Participants

Athletes with groin pain are consecutively recruited from two clinics of a visceral surgeon specialized in groin pain in athletes. The clinics are located in Bordeaux and Paris, France, and patient population includes athletes from all over France. Inclusion criteria are: adult (>18 years old) athletes with adductor-related groin pain, subcategorized as adductor longus insertion pain, undergoing unilateral or bilateral adductor longus tenotomy by one visceral surgeon specialized in groin pain in athletes.

Adductor-related groin pain is clinically diagnosed as adductor tenderness and pain on resisted adduction testing as described in the Doha agreement on terminology and definitions of groin pain in athletes.[8] For this study, we further specified both palpation and resistance pain should be present at the proximal adductor longus insertion. No specific exclusion criteria were present other than refusal to participate in the study. As the vast majority of patients seen in the clinic are male athletes, we based our sample size calculation and primary analysis on male athletes only. The results from any female athletes included during the same period will be reported separately as a secondary analysis.

Ethics

Ethics approval was obtained by the ethics committee of Clinique du sport de Bordeaux-Merignac, France (#02-2020.2). Athletes will be included in this study after giving their informed consent according to the Declaration of Helsinki.

Patient demographics and injury information.

Demographic data (age, height, weight, type and level of sport) is recorded. Athletes are also asked about the duration of their groin pain (weeks), the onset of pain (sudden/gradual), whether the pain is unilateral or bilateral, highest pain during their last session of sports on a 0-10 numerical pain rating scale (NPRS, 0 being 'no pain' and 10 'worst pain imaginable'). They will also be asked if they have any pain in other locations than the groin.

Bent knee fall out test (BKFO)

The BKFO test is performed in either general anesthesia or spinal anesthesia, for patients operated in Bordeaux and Paris, respectively. This is standard procedure for the surgical procedures and also prevents any voluntary activation of the adductor muscles. The patient lies supine on the surgical table with approx. 90° knee flexion, 45° hip flexion, and the feet together and the hips in external rotation (also known as the frog-leg position). Standardization of position is achieved by flexing one leg first, so the medial malleolus is placed next to the medial knee joint line of the contralateral leg. The knee is then moved laterally, externally rotating the hip with the plantar surface placed towards the contralateral leg. The contralateral leg is then flexed, and the plantar surfaces of the feet are aligned. The distance between the most distal point on the head of the fibula and the surface of the surgical table is measured using a rigid tape measure and distance is recorded in cm to the nearest 0.5 cm (Figure 1) The BKFO test has excellent reproducibility with a standard error of the measurement of approx 1 cm or less.[4,11,12]

[figure not shown]

Figure 1 A: Position of the patient's legs prior to the surgical procedure, B: Measurement from the head of the fibula to the surgical table

Surgical procedure

The proximal adductor longus tendon is identified through palpation, and a longitudinal incision of approximately 4cm is made in the line of the tendon. The fascia of the adductor longus is divided to identify the tendon (figure 2), and a transverse incision is made as close to the insertion as possible (approximately 0.5cm) resulting in a full release of both the adductor longus tendon and muscle, as present on the posterior side of the tendon. A minor removal of approximately 0.5 cm of the released tendon is made, and the adductor longus is placed approximately 5 cm from the pubic bone (figure 2). The wound is closed in layers after careful hemostasis. The tenotomy is either performed unilateral or bilateral.

[figure not shown]

Figure 2 Adductor longus tendon before and after the tenotomy.

Statistical analysis

Data are presented as means with standard deviation (SD), unless indicated otherwise, and non-normally distributed data are expressed as medians with the 25th–75th interquartile range (IQR₂₅, IQR₇₅). A paired T-test is used to compare the BKFO results pre- and post- tenotomy. Additionally, correlation between baseline values and change in BKFO will be analyzed to investigate whether patients with higher baseline test results also have a larger change. Analyses are carried out in Statistical Package for Social Sciences (SPSS; version 21, IBM). Effect sizes were calculated using Cohen's d and assessed as; small ($d = 0.2$), moderate ($d = 0.5$), and large ($d = 0.8$).[13]

Sample size

We calculated our sample size using G*power software (v. 3.1, Heinrich-Heine-Universität, Düsseldorf, Germany). We used BKFO values from non-injured football players; mean 13.1 cm, standard deviation (SD) 4.4cm.[4] We performed pilot measurements pre- and post-tenotomy on five patients. These had a

mean of 2.1 cm reduction, which we used for the sample size calculation. We set the required power at 95%, used an α -error probability of 5%, and a correlation between measurements of 0.5. This resulted in a total sample size requirement of 60 participants.

REFERENCES

- 3 Hölmich P. Long-standing groin pain in sportspeople falls into three primary patterns, a “clinical entity” approach: a prospective study of 207 patients. *Br J Sports Med* 2007;**41**:247–52. doi:10.1136/bjism.2006.033373

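### Anaesthesia type coincides with clinic and both clinics are pooled without a clinic term; the paired test is unaffected, but the baseline-change correlation should be adjusted for clinic and results shown by clinic (low severity)

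*Combined protocol and SAP*

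**What the plan says.** On recruitment (Participants): "Athletes with groin pain are consecutively recruited from two clinics of a visceral surgeon specialized in groin pain in athletes". One surgeon operates at both sites. The expected split of patients between Bordeaux and Paris is not given.

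On measurement (Bent knee fall out test): "The BKFO test is performed in either general anesthesia or spinal anesthesia, for patients operated in Bordeaux and Paris, respectively". The section adds: "This is standard procedure for the surgical procedures and also prevents any voluntary activation of the adductor muscles". It does not say that the two types of anaesthesia give the same passive BKFO value or the same change.

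On analysis (Statistical analysis): "A paired T-test is used to compare the BKFO results pre- and post- tenotomy". In addition, "correlation between baseline values and change in BKFO will be analyzed to investigate whether patients with higher baseline test results also have a larger change". Cohen's d is the only other statistic named. The only planned split is by sex, with male athletes as the primary analysis. Clinic and anaesthesia are not mentioned in the Statistical analysis or Sample size sections.

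**The concern.** Pairing removes differences in level between patients, and so between clinics, from the comparison of pre with post. It does nothing for the second analysis, which asks whether patients who start higher change more. If one clinic had both a higher mean baseline and a larger mean change, pooling would add a positive component to the correlation. If the two differences ran in opposite directions, it would add a negative one. Neither component says anything about tight versus flexible patients.

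A smaller issue concerns the mean change. The Introduction wants to know how much the muscle contributes to the test. If the tenotomy effect differed between the two measurement conditions, the pooled mean would be an average weighted by however many patients each clinic enrolled, and no planned output would show this.

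**Working it through.** **Inputs from the plan (Sample size; BKFO section).** Baseline: "mean 13.1 cm, standard deviation (SD) 4.4cm". Effect: "mean of 2.1 cm reduction, which we used for the sample size calculation". Pre-post correlation 0.5, α 5%, power 95%, N = 60. Standard error of measurement (SEM) about 1 cm or less.

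**Assumptions, not in the documents.** A 50:50 clinic split; a between-clinic difference of 2.2 to 4.4 cm at baseline (0.5 to 1 SD) and 1 to 2 cm in mean change; no correlation within clinic.

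**Step 1: the plan's own figure.** SD of change = 4.4 × √(2 × (1 − 0.5)) = 4.4 cm, so dz = 2.1/4.4 = 0.477. The two-sided paired t-test (noncentral t) has power 0.9531 at n = 60 and 0.94998 at n = 59. The stated 60 is reproduced.

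**Step 2: two values for the SD of change.** The plan's inputs imply 4.4 cm. As a lower extreme, if all variation in change were measurement error with SEM 1 cm, the SD would be √2 × 1 = 1.41 cm.

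**Step 3: correlation induced by clinic alone.** With p the share of patients at one clinic, and b and c the clinic differences in baseline and change in within-clinic SD units,

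r = p(1−p)·b·c / √[(1 + p(1−p)b²)(1 + p(1−p)c²)].

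Example, smallest differences at SD 4.4: b = 0.5, c = 1/4.4 = 0.227, so r = 0.25 × 0.5 × 0.227 / √(1.0625 × 1.0129) = 0.0284/1.037 = 0.03.

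Example, largest differences at SD 1.41: b = 1, c = 2/1.41 = 1.414, so r = 0.354/√(1.25 × 1.5) = 0.26.

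The chance of p < 0.05 at n = 60 uses the Fisher approximation: z = atanh(r) × √57, compared with ±1.96.

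| Baseline diff. | Change diff. | r (SD 4.4) | chance | r (SD 1.41) | chance |
|---|---|---|---|---|---|
| 2.2 cm | 1 cm | 0.03 | 5.5% | 0.08 | 9% |
| 2.2 cm | 2 cm | 0.05 | 7% | 0.14 | 19% |
| 4.4 cm | 1 cm | 0.05 | 7% | 0.15 | 21% |
| 4.4 cm | 2 cm | 0.10 | 12% | 0.26 | 51% |

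At an 80:20 split, p(1−p) falls from 0.25 to 0.16, and the largest values fall to 0.07 (SD 4.4) and 0.18 (SD 1.41).

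**Step 4: coupling, which is present inside each clinic.** With equal pre and post SDs and pre-post correlation ρ, the correlation of baseline with reduction is √((1−ρ)/2). The plan's ρ = 0.5 gives √0.25 = 0.50. An SD of change of 1.41 cm with SDs of 4.4 cm gives 1.41/(2 × 4.4) = 0.16. Starting from 0.50 within clinic, pooled r runs from 0.35 to 0.54 over baseline differences of 1 to 4 cm, change differences of −2 to +2 cm, and splits from 50:50 to 80:20.

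**Step 5: the mean change.** A 1 cm clinic difference in effect moves the pooled mean by (0.8 − 0.5) × 1 = 0.3 cm between a 50:50 and an 80:20 mix, which is 14% of 2.1 cm. A pooled 2.1 cm with a 2 cm difference at 50:50 means 3.1 and 1.1 cm. The SD of the pooled changes is then √(4.4² + 0.25 × 2²) = 4.51 cm and the power of the pooled test is still 94%, so a significant pooled result would not reveal the difference.

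**Step 6: precision of a clinic comparison.** The 95% CI half-width at 30 per clinic is t(58) × SD × √(1/30 + 1/30) = 2.00 × SD × 0.258. This is 0.7 cm at SD 1.41 and 2.3 cm at SD 4.4. Power for a 2 cm difference at SD 4.4 is 41%.

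**The case against.** The strongest reply is that nothing in the documents suggests that the clinics differ. The same surgeon operates at both, the position and measurement are standardised, patients come from all over France, and voluntary muscle activation is said to be prevented under either anaesthetic. Bias in the correlation needs a difference in baseline and a difference in change together. A 2 cm difference in change would be almost the whole planned effect. This stands, and it is why the point is of low severity. It does not close the point, because preventing voluntary activation is not the same as giving equal passive readings, and the plan has no output that would check this.

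The second reply is that, if the plan's inputs hold, the correlation within clinic is already about 0.50 through coupling. The pooled range of 0.35 to 0.54 then lies wholly above the critical value of 0.254 at n = 60, so clinic would neither create nor hide the relation. This also stands. Clinic would alter the size of the coefficient in that setting, but coupling is the larger problem and a clinic term leaves it in place.

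The third reply is that any consecutive series averages over its case mix. This largely stands. The 0.3 cm shift in Step 5 is about a quarter of the pooled 95% CI half-width of 1.14 cm at SD 4.4.

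A reader might go further and infer that the primary result is confounded by anaesthesia. The documents do not support that, because both measurements in each patient are taken under the same anaesthetic. A reader might also infer that clinic would produce a spurious significant correlation about half the time. That holds only in the bottom right corner of the table: a full-SD baseline difference, a 2 cm difference in change, an even split and pure measurement error.

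**Conclusion.** The point holds as an inexpensive improvement of low severity. Anaesthesia is tied one-to-one to clinic, and the planned correlation pools the clinics without adjustment. The paired t-test is valid and should remain primary.

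Under the assumed clinic differences and no within-clinic correlation, the induced r is 0.03 to 0.10 at the plan's implied SD of change, with a 5.5% to 12% chance of p < 0.05 against a nominal 5%. The value of 0.26 is an extreme case. The actual split and clinic differences are unknown, so these figures bound what could happen under stated assumptions and do not estimate a bias that is present.

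For the mean change the issue is only what the average represents if the effects differ, not the validity of the test.

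**What to change.** Keep the paired t-test as the primary analysis. Add to the Statistical analysis section:

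1. A descriptive report, by clinic/anaesthesia group, of baseline BKFO and mean change with its 95% CI, and the between-group difference in change with its 95% CI.
2. The baseline-change association estimated with a clinic term, by partial correlation or regression.
3. A statement that clinic and anaesthesia effects cannot be separated in this design.
4. A statement that the clinic term does not remove the mathematical coupling between baseline and change, which needs its own remedy.

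The cost is a few lines of text and one degree of freedom. Each patient's clinic is already known and N stays at 60. The smallest correlation detectable with 80% power moves from tanh(2.80/√57) = 0.355 to tanh(2.80/√56) = 0.358. The downside is an imprecise between-clinic comparison, with a half-width of about 0.7 to 2.3 cm at 30 per clinic and wider at an uneven split (2.8 cm at 48/12 with SD 4.4). It should be labelled descriptive, and a non-significant difference should not be read as evidence that the two conditions are equivalent.

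### The plan does not hide the first BKFO value or the tape scale at the second reading, so any reading bias adds directly to the uncontrolled mean change

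*Combined protocol and SAP*

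**What the plan says.** The section on the bent knee fall out test sets out the position of the legs, the bony landmark and the instrument. The distance is "measured using a rigid tape measure and distance is recorded in cm to the nearest 0.5 cm". It adds: "The BKFO test has excellent reproducibility with a standard error of the measurement of approx 1 cm or less". General or spinal anaesthesia is noted as preventing voluntary muscle activity by the patient.

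The section does not say who positions the leg, who reads the tape, whether one person takes both readings, or whether the first value is out of sight at the second. No masking of any kind appears in the document.

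Under Statistical analysis, the comparison is within one group: "A paired T-test is used to compare the BKFO results pre- and post- tenotomy". Some tenotomies are unilateral, but no use of the unoperated side as a control is planned. The Sample size section takes its effect from five pilot patients, with a "mean of 2.1 cm reduction, which we used for the sample size calculation".

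**The concern.** A hand-read distance on a leg that staff have positioned leaves room for judgement, and the expected direction is known in advance. The Introduction links a high result to adductor tightness, which the operation is meant to remove, and the pilot showed a reduction. A measurer who remembers the first value, or who can see the scale while knowing that the tendon has been cut, may settle on the lower of two plausible readings.

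With a control group, a bias common to both arms would cancel. Here nothing cancels it. A systematic shift of b cm in the second reading moves the estimated mean change by b cm, and recruiting more patients only makes the biased estimate more precise. The stated aim is to learn both whether the muscle affects the test and by how much, and a shift affects both answers. It cannot be corrected in the analysis once the readings have been taken.

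**Working it through.** **Inputs from the plan.** Single-reading SD 4.4 cm ("We used BKFO values from non-injured football players; mean 13.1 cm, standard deviation (SD) 4.4cm"), correlation 0.5, mean reduction 2.1 cm, alpha 5%, power 95%, n = 60 (Sample size section); recording grid 0.5 cm and SEM about 1 cm or less (BKFO section).

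**The plan's own figure.**
- SD of change = √(2 × 4.4² × (1 − 0.5)) = 4.4 cm.
- Standardised effect = 2.1 / 4.4 = 0.477.
- The noncentral t, two-sided at 5%, gives 94.998% power at n = 59 and 95.3% at n = 60. The stated 60 is reproduced. A one-sided test would need 49, so the two-sided reading is used below.

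**Does the recording rule bias the mean?** Two million simulated pairs (first reading with mean 13.1 and SD 4.4; change with mean −2.1 and SD 4.4) had a mean change of −2.094 cm unrounded and −2.094 cm after rounding both readings to the nearest 0.5 cm. The SD moved only from 4.402 to 4.407. Applied as written, the rule does no harm.

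**Size of directional rounding (assumed worst case).** If the second reading is always rounded down on a 0.5 cm grid, the average shift is 0.5 / 2 = 0.25 cm. The simulation agrees: −2.344 against −2.094. As a share of the planned effect, 0.25 / 2.1 = 12%.

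**False-positive rate at n = 60, true change zero, shift 0.25 cm.** The noncentrality is 0.25 × √60 / SD, on 59 degrees of freedom, with critical value 2.001. The smallest significant mean change is 2.001 × SD / √60.

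| SD of change (cm) | Where it comes from | Noncentrality | Smallest significant mean change (cm) | Rejection rate |
|---|---|---|---|---|
| 4.4 | planning inputs | 0.44 | 1.14 | 7.2% |
| 3.0 | assumed, intermediate | 0.65 | 0.77 | 9.7% |
| 2.0 | assumed, intermediate | 0.97 | 0.52 | 15.9% |
| 1.41 | √2 × SEM of 1 cm, measurement error only | 1.37 | 0.37 | 27.0% |

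Without the shift, every row would be 5%.

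**Effect of finer reading.** On a 0.1 cm grid the same worst case is 0.1 / 2 = 0.05 cm.

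**The case against.** The strongest reply is that the written rule is unbiased and that every figure above supposes a measurer who breaks it in the same direction in every patient. That is correct. The 0.25 cm is a ceiling for directional rounding of the second reading, not an estimate. Nor does the SEM of about 1 cm help either side: it describes random error and neither supports nor excludes a systematic shift.

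A reader might infer a larger effect by supposing that the first reading is also rounded up. The total would then be 0.5 cm (24% of 2.1 cm), with rejection rates of 13.9% at SD 4.4 cm and 76.8% at SD 1.41 cm. Those figures do not follow from the gap described here, because knowing the first value cannot influence the first value. The 1.41 cm SD is itself a limit that allows no variation between patients in true change. It is most relevant if the tenotomy truly does nothing, but the plan's own inputs point to 4.4 cm, where the rise is from 5% to 7%.

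It is also fair to say that the p-value is not the only output. The plan reports means with SD and Cohen's d, and a pure 0.25 cm shift gives d = 0.25 / 4.4 = 0.06 or 0.25 / 1.41 = 0.18, both below the plan's threshold for a small effect. This limits the harm to interpretation, but the estimate is still shifted.

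Finally, a reader might infer that masking would prevent the bias at no cost in staff. The documents support neither part. The measurer still knows that the second test follows the operation, so expectation can still act through leg positioning. The documents also say nothing about theatre staffing.

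**Conclusion.** The point holds as a design weakness worth correcting. The measurement section is complete as a procedure, yet it leaves the first value and the scale open to the person taking the second reading. The uncontrolled paired analysis passes any resulting shift into the estimate in full.

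In the assumed worst case for directional rounding of the second reading, the shift is 0.25 cm, and the false-positive rate is 7% at the planning SD and 27% in the measurement-error-only limit. These figures rest on n = 60, a two-sided 5% test, no true change, and a shift whose size the documents do not give. Bias through leg positioning would come on top, and no figure for it is available. The documents show that the trial is exposed to this bias, not that the bias occurs.

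**What to change.** Add to the BKFO section:
- The same measurer takes both readings in a patient.
- At each test the position is marked on a fresh unnumbered strip, or on a tape with its scale turned away from the measurer.
- The mark is read afterwards to the nearest 0.1 cm. Where feasible, the strip is coded so that the reader does not know whether it is the pre- or post-tenotomy mark.
- The first value is not disclosed until the second has been recorded.
- The measurer remains aware of tenotomy status, so bias from leg positioning is not removed; the report should say so.

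The cost is a wording change and slightly more handling at each reading. Strips read later avoid the need for a second reader at the table. The sample size stays at 60 and the planned analysis is unchanged. The residual positioning bias is the price of a design in which the operation cannot be hidden from the measurer. The change has to be made before readings are taken.

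### Does the paired t-test need a stated unit of analysis for patients operated on both sides?

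*Combined protocol and SAP*

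**What the plan says.** The Participants section includes athletes "undergoing unilateral or bilateral adductor longus tenotomy", and the Surgical procedure section repeats that "The tenotomy is either performed unilateral or bilateral". The Bent knee fall out test section defines the outcome at a single leg: "The distance between the most distal point on the head of the fibula and the surface of the surgical table is measured". It describes one distance and does not say whether both legs are measured in a bilateral case.

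The Statistical analysis section gives the primary comparison in one sentence: "A paired T-test is used to compare the BKFO results pre- and post- tenotomy". It adds a correlation between baseline and change, to see "whether patients with higher baseline test results also have a larger change", and Cohen's d. The Sample size section takes an SD of 4.4 cm, a mean reduction of 2.1 cm from a pilot of five patients, a correlation of 0.5 between measurements, 95% power and 5% alpha, and concludes: "This resulted in a total sample size requirement of 60 participants". No sentence says how a bilateral patient's two legs become the value that is analysed.

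**The concern.** A bilateral patient can supply two pre/post pairs, taken in one linked frog-leg position. A paired t-test deals with the pairing of before and after. It does not deal with two legs belonging to one person. If every operated leg were a separate row and the legs' changes were positively correlated, the test would treat the data as more informative than they are, and both the standard error and any interval would be too narrow. If only one leg were used with no rule fixed beforehand, it could be chosen after both had been seen, which could bias the mean change.

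The Introduction promises that "we will be able to show if and how much the flexibility of this muscle effects the test results". The size and precision of the mean change are therefore the main product of this single-group study, and an unstated unit appears to leave them open.

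**Working it through.** **Inputs from the plan.** SD 4.4 cm, mean change 2.1 cm, pre/post correlation 0.5, power 95%, alpha 5% (sidedness not stated), 60 participants.

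**Inputs assumed.** The share of bilateral patients, b, and the correlation of change between a patient's two legs, ρ. The documents give neither, so a range is shown for each.

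**1. The plan's own figure.** SD of change = 4.4 × √(2 × (1 − 0.5)) = 4.4 cm. Standardised effect = 2.1 / 4.4 = 0.477. The exact two-sided paired t-test first reaches 95% power at n = 60 (power 0.953). A one-sided test would need 49. The stated 60 therefore matches a two-sided test on 60 independent changes, one per participant.

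**2. One value per participant.** With the mean of the operated legs as the value, simulation (200,000 runs per cell; b of 10, 25, 50, 75 and 100%; ρ of 0, 0.1, 0.3, 0.5 and 0.8) gives a type I error of 4.9% to 5.1% throughout. The mix of one-leg and two-leg values does not upset the test. With a preset index leg there is simply one change per person, as in the sample-size calculation.

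**3. Legs entered as independent pairs.** The variance of the mean is understated by the design effect 1 + 2bρ / (1 + b). At b = 0.5 and ρ = 0.5 this is 1 + 0.5 / 1.5 = 1.33, so the true SE is √1.33 = 1.15 times the reported one. Simulated type I error against a nominal 5%:

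| Bilateral share | ρ = 0 | ρ from 0.1 to 0.8 |
|---|---|---|
| 10% | 5.0% | 5.3% to 6.7% |
| 25% | 5.0% | 5.5% to 8.8% |
| 50% | 5.0% | 5.8% to 11.3% |
| 100% | 5.0% | 6.2% to 14.4% |

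**4. Effect on the conclusion at the planned effect.** Corrected t = 2.1 / (4.4 × √(design effect / legs)). The smallest value over the 25 scenarios is at b = 0.25 and ρ = 0.8. There are 75 legs, the design effect is 1 + 0.4 / 1.25 = 1.32, and t = 2.1 / (4.4 × √(1.32 / 75)) = 3.60.

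**5. Effect on precision (b = 0.5, ρ = 0.5).**
- By leg, uncorrected: 1.99 × 4.4 / √90 = 0.92 cm.
- By participant mean: SD = 4.4 × √(0.5 + 0.5 × 0.75) = 4.12 cm, so the half-width is 2.00 × 4.12 / √60 = 1.06 cm.
- Difference: 1.06 − 0.92 = 0.14 cm. Each distance is recorded to the nearest 0.5 cm, and the plan does not call for a confidence interval.

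**6. Dependence on the planning SD.** The 4.4 cm SD of change combines the SD of uninjured players with an assumed correlation of 0.5. The protocol puts the standard error of measurement at about 1 cm or less, so a higher same-session correlation is plausible. At 0.9 (an assumption) the SD of change is 4.4 × √(2 × 0.1) = 1.97 cm. The two half-widths become about 0.41 and 0.47 cm. Ratios of SEs and type I error do not change.

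**The case for a change.** The best case for acting is that participant wording fixes how many people are recruited, not what number each contributes. Even if one value per patient is intended, the text does not say which leg, or what average, represents a bilateral patient. The gap also touches the baseline-change correlation and Cohen's d, and one or two sentences would close it. That much stands: no section contains the rule.

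The consequences offered in support are weaker.

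- **Type I error.** The inflation belongs to a leg-level analysis that no section describes. The largest figure, 14.4%, also needs every patient to be bilateral and ρ = 0.8.
- **Power.** If the target of 60 were filled with legs, power could fall to between 0.93 and 0.74 (b from 0.25 to 1.0, ρ from 0.3 to 0.9). The Sample size section counts participants, which rules this out.
- **Choosing the leg afterwards.** If the leg with the larger change were always picked, the bias would be b × 4.4 × √((1 − ρ) / π). At b = 0.5 that is 0.56 cm (ρ = 0.8) to 1.24 cm (ρ = 0). This requires both legs to be measured, one to be analysed, and the favourable one to be taken every time. Nothing in the plan suggests it, and a random or preset leg carries no such bias.
- **Cohen's d.** At b = 0.5 and ρ = 0.5, d is 2.1 / 4.4 = 0.48 by leg and 2.1 / 4.12 = 0.51 by participant mean. They straddle the 0.5 benchmark only because the planning value lies beside it. With a pre/post correlation of 0.9 they would be 1.07 and 1.14, both above 0.8. The two are also on different scales, and no decision hangs on the benchmark.

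**Conclusion.** The omission is real, but it is missing detail and not a wrong method. The sample size, the pilot and the correlation analysis are all worded by participant or patient, and the stated 60 reproduces exactly on one independent change per participant. On that reading the paired t-test holds its level, whether a bilateral patient is represented by the mean of the operated legs or by an index leg set in advance. The choice between those two is largely a matter of preference.

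Harm arises only if the analyst departs from that reading, and its size then rests on a bilateral share and a between-leg correlation that the documents do not give. In the middle scenario (50% and 0.5) the SE would be understated by a factor of 1.15, and the half-width would be 0.14 cm narrower than by participant mean. At the planned effect and SD, significance survives in all 25 scenarios. A competent analyst would work at participant level and report the numbers of patients and legs as a matter of course. No change to the plan follows.

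### Does leaving the divisor of Cohen's d unnamed make the small, moderate or large grading unsafe?

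*Combined protocol and SAP*

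**What the plan says.** The Statistical analysis section sets out the primary comparison: "A paired T-test is used to compare the BKFO results pre- and post- tenotomy". Data are to be shown as means with SDs, or as medians with quartiles where the distribution is not normal, and the change in BKFO is also to be correlated with its baseline value. The effect-size sentence follows: "Effect sizes were calculated using Cohen's d and assessed as; small" at 0.2, moderate at 0.5 and large at 0.8, with a literature reference. Neither this section nor any other names the divisor of d.

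The Sample size section takes "mean 13.1 cm, standard deviation (SD) 4.4cm" from non-injured football players. It adds a pilot "mean of 2.1 cm reduction, which we used for the sample size calculation" (five patients), "a correlation between measurements of 0.5", 5% alpha and 95% power, and arrives at 60 participants. The Introduction gives the purpose: "we will be able to show if and how much the flexibility of this muscle effects the test results".

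**The concern.** With paired data, d has at least two common forms. One divides the mean change by the spread of BKFO between athletes (the baseline SD, or an average of the pre and post SDs). The other, usually written dz, divides it by the SD of the individual changes. If the pre and post SDs are equal, the two coincide only at a correlation of 0.5. That is the planning value, so the sample-size figures cannot show which form is meant.

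The forms answer different questions. The first sets the shift against how much athletes differ from one another. The second measures how consistent the shift is, and it rises as the test becomes more repeatable even when the change in centimetres stays the same. The section on the BKFO test cites a standard error of measurement of about 1 cm or less, so a correlation above 0.5 is plausible. The same 2.1 cm could then be called large under one form and about moderate under the other. A reader could take a large dz to mean that BKFO mainly reflects the adductor longus. An unnamed divisor could also be chosen after the data are seen.

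**Working it through.** **Inputs.** Mean change 2.1 cm, SD 4.4 cm, correlation r = 0.5, alpha 5%, power 95% and N = 60 are from the Sample size section. The standard error of measurement (SEM), about 1 cm, is from the BKFO section. Equal pre and post SDs, and every r other than 0.5, are assumptions.

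**Step 1: the plan's own figure.** SD of change = SD × √(2(1 − r)) = 4.4 × √(2 × 0.5) = 4.4 cm. Hence dz = 2.1/4.4 = 0.477. The exact paired t-test calculation (noncentral t, two-sided 5%, 95% power) gives n = 60, with power 95.3% at 60. The stated total is reproduced. A one-sided test would give 49, so the two-sided reading is the one that fits.

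**Step 2: the two forms of d for the same 2.1 cm.** d on the raw SD = 2.1/4.4; dz = 2.1/(4.4 × √(2(1 − r))).

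| r | SD of change (cm) | d on raw SD | dz |
|---|---|---|---|
| 0.3 | 5.21 | 0.477 | 0.403 |
| 0.5 | 4.40 | 0.477 | 0.477 |
| 0.7 | 3.41 | 0.477 | 0.616 |
| 0.8 | 2.78 | 0.477 | 0.755 |
| 0.9 | 1.97 | 0.477 | 1.067 |

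dz reaches a value k at r = 1 − (2.1/(4.4k))²/2, which is r = 0.544 for k = 0.5 and r = 0.822 for k = 0.8. The correlation matters only if dz is the form used.

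**Step 3: how high could r be?** Suppose a 1 cm SEM carried over to the pre-post pair and every patient responded identically. Then r = 1 − 1²/4.4² = 0.948, the SD of change is √2 = 1.41 cm, and dz = 2.1/1.41 = 1.48. That is an upper-end case for a 1 cm SEM, because it leaves no room for patients to differ in their response. With a between-patient response SD of t, the SD of change is √(2 + t²). dz is below 0.8 when this exceeds 2.1/0.8 = 2.625 cm, that is when t > √(2.625² − 2) = 2.2 cm. The documents give no value for t.

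**Step 4: what depends on the divisor?** The paired t statistic is dz × √n whichever d is printed, so the test, its p-value and the sample size do not move. Both forms can also be recovered from ordinary paired output. The pre and post means with the pre SD give d on the raw SD, and t/√n gives dz. At the planning values, t = 0.477 × √60 = 3.70, and 3.70/√60 returns 0.48.

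**The case for a change.** The best case for acting is that the study asks how much the muscle contributes, and the d scale is the only yardstick the plan offers for judging size: it states neither a confidence interval nor an important difference in centimetres. A divergence in labels is also realistic. With a 1 cm SEM, the response to tenotomy would need an SD above 2.2 cm, more than the mean change itself, to keep dz below 0.8. Naming the divisor would cost one sentence and remove a choice made after the data are seen.

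Much of this stands. The divisor is missing, the arithmetic is right, and a large dz is possible. The consequence is weaker than it sounds. BKFO is recorded in centimetres and summarised as means with SDs, so the size of the shift can be read without d. No decision rule or claim is attached to the label, and the Introduction says only that the result should help later thinking about what the test measures. Neither form of d estimates the share of BKFO due to the adductor longus. Nor is a response SD above 2.2 cm ruled out: the plan includes unilateral and bilateral operations and itself looks at whether change varies with baseline. Finally, the three values may be read as benchmarks rather than thresholds. In that case 0.48 is simply moderate, and the contrast with dz = 0.75 at r = 0.8 is mild.

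**Conclusion.** No change to the plan follows. The effect-size sentence omits a definition; it does not state a rule that gives a wrong answer. For a 2.1 cm change the reported d could be 0.48 on the raw SD, or above 0.8 on the SD of change if the correlation exceeds about 0.82. That range assumes equal pre and post SDs and a correlation that the documents do not supply. It affects a descriptive label only; the paired t-test and N = 60 are untouched.

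The choice among baseline SD, average SD and SD of change is one on which competent statisticians differ, so there is no single correct divisor that the plan has missed. An analyst has to choose one to compute d at all, and would ordinarily name it beside the mean change in centimetres. This is a gap that sensible reporting fills.
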